# 6.7.1.5. Days of Absence from Work/School Related to Adjudicated PEs per Patient Year Over the 52 Week Treatment period

To get the number of days absent from work/school the CRF "Missed work/school YN" will be used. Data will only be gathered if both questions "Is the subject currently working or attending school?" and "Has the subject missed any days of work/school since the last visit due to reasons related to bronchiectasis symptoms?" are answered with "Yes".

Missed days of work/school will be identified through the CRF "Missed work/school log". The recorded number of days in the CRF field "How many days?" will be used. The number of days absent from work/school will be linked to the adjudication outcome. Days of absence will be summarized only.

The number of days missed work/school due to adjudicated PEs per year is calculated as total number of days missed by the total time on treatment:

$$(\textit{days missed per person\_year})_{trt} = \frac{\sum (\textit{days missed})_{i,trt}}{\sum \textit{time\_on\_treatment}_{i,trt}(\textit{years})},$$

where i describes the participant of  $trt \in \{\text{brensocatib 10mg, brensocatib 25mg or placebo}\}$ . The total time on treatment in days will be calculated for each treatment (trt) by pooling all patients time on treatment in years together.

CONFIDENTIAL Page 40 of 139

#### 6.7.1.6. Time to First Pulmonary Exacerbation

The time to first exacerbation event confirmed through adjudication will be calculated as

```
Time to first PE (days) = CEC assessed onset date of first PE - date of reference* + 1.
```

\*For the On-Study Estimand the date of reference will be the date of randomization, while for the On-Treatment Estimand the date of reference will be the date of first IP administration (see Sections 6.4.1 and 6.7).

Participants who do not have a PE confirmed through adjudication during the 52-week treatment period or for whom the first PE is recorded beyond Week 52 visit will be censored at the date of Week 52 (or at the date of EOS for participants early discontinued from study) visit for the On-Study Estimand and at the date of last IP intake or the date of first ICE onset for the On-Treatment Estimand. Participants randomized but not treated will not be analyzed for the On-Treatment Estimand but censored at the day of randomization.

#### 6.7.1.7. Reporting of Pulmonary Exacerbations in Study Months

The onset date of a PE will determine the assignment into the "Study Months". The reference date for On-Study estimand will be the date of randomization. Technical instructions given below:

The variable PULMDT describes the PE onset date and the variable RANDDT the date of randomization.

#### 6.7.2. Responder Status for Exacerbation-Free over the 52-Week Treatment Period

For the On-Study Estimand, a participant will be defined as "Responder" / "Non-responder" based on exacerbation events that are confirmed through adjudication over the 52-week treatment period.

In order, to be a "Responder" participants must:

- complete 52-Weeks on study, AND
- have no exacerbation event that meets the protocol definition of PE diagnosis confirmed by an independent adjudication committee during the 52-Weeks.

If a participant has at least one PE confirmed through adjudication during the 52-Week study period, the participant will be classified as "*Non-responder*".

CONFIDENTIAL Page 41 of 139

For participants who discontinue the study prior to Week 52 without having experienced a PE confirmed through adjudication, their responder status will be imputed based on the observed data model (see Section 8.3.2.1).

For the Composite Estimand, the above criteria must be met, at a minimum, in order to be classified as "*Responder*". However, participants meeting one of the below criteria will be considered as "*Non-responder*", given no PE was observed prior to:

- Early discontinuation from randomized IP for the below reasons:
  - o Death due to NCFBE (to be investigated through the AE page)
  - Lack of efficacy
  - Tolerability; defined as discontinuation from randomized IP due to an AE which is deemed to be related to the randomized IP by the investigator; cases will be identified through the AE eCRF by looking for action="DRUG WITHDRAWN", relationship="RELATED"
- Addition of chronic antibiotics over the 52-Week Treatment Period

Early discontinuation from randomized IP for other reasons will follow the Treatment Policy strategy.

# 6.7.3. Change from Baseline in Pulmonary Function Test Parameters and Rate of Change in FEV1 (Pre- and Post-bronchodilator)

Prebronchodilator and postbronchodilator pulmonary function test (PFT) parameters will be determined by spirometry. To ensure quality control, all spirometry's are reviewed independently to ensure that they meet ATS/ERS acceptability criteria (see CSP Section 7.3). Only those spirometry tracings determined to be acceptable, or borderline will be used, based on the best effort selected by ERT per spirogram. If more than one best effort was recorded for each of multiple screening visits, the last record will be used for the analysis. Optional PFT assessments will be excluded from all analysis but listed only. They will not be considered for the determination of baseline.

The baseline will be derived as the most recent pulmonary function test parameter assessment (separately for prebronchodilator and postbronchodilator) prior to first administration of randomized IP using measurements determined as best effort and selected for the analysis, e.g., the last measurement in case of multiple screening visits.

The absolute change from baseline at Week X will be calculated as (definition shown for FEV1 only but applies the same for all pulmonary function test parameters):

$$FEV_{1,Change\ from\ Baseline\ at\ Week\ x} = FEV_{1,Week\ x} - FEV_{1,Baseline}.$$

## Percentage Change from baseline in FEV1

The percentage change in from baseline in FEV1, separately for prebronchodilator and postbronchodilator, will be calculated as

$$FEV_{1,change\ from\ baseline}(\%) = \left(\frac{FEV_{1,Week\ x}}{FEV_{1,Baseline}} - 1\right) * 100.$$

CONFIDENTIAL Page 42 of 139

# 6.7.4. Annualized Rate of Severe Pulmonary Exacerbation Events that Meet the Protocol Definition of PE Diagnosis

A severe exacerbation event that meets the protocol definition of PE diagnosis is defined as a PE requiring IV antibacterial drug treatment and/or hospitalization and must also be confirmed as severe through the event adjudication process.

The same derivation rules will be used as for Annualized Rate of PEs (see Section 6.7.1.2) with the exception, the PEs will be limited to severe PEs only.

### 6.7.5. Patient-Reported Outcomes

Patient-Reported Outcomes data will be collected via an electronic patient-reported outcome device (ePRO device). Age-dependent questionnaires, e.g., QoL-PCD, will remain throughout the study regardless of a change in participant's age.

#### **6.7.5.1.** Windowing

QoL-B, PGI-S, and PGI-C will be completed every 2nd week. To allocate data correctly, biweekly periods are defined in Table 6, where Day 1 is the day of randomization.

Table 6: Bi-Weekly Windowing for PRO assessments

Period	Bi-Weekly (Days)*	Target Date for	Label in data tabulations
		Assessment	
Baseline	Day 1		Baseline
1	Day 2 – Day 22	Day 15	Week 2
3	Day 23 – Day 36	Day 29	Week 4
3	Day 37 – Day 50	Day 43	Week 6
4	Day 51 – Day 64	Day 57	Week 8
5	Day 65 – Day 78	Day 71	Week 10
6	Day 79 – Day 92	Day 85	Week 12
7	Day 93 – Day 106	Day 99	Week 14
8	Day 107 – Day 120	Day 113	Week 16
9	Day 121 – Day 134	Day 127	Week 18
10	Day 135 – Day 148	Day 141	Week 20
11	Day 149 – Day 162	Day 155	Week 22
12	Day 163 – Day 176	Day 169	Week 24
13	Day 177 – Day 190	Day 183	Week 26
14	Day 191 – Day 204	Day 197	Week 28
15	Day 205 – Day 218	Day 211	Week 30
16	Day 219 – Day 232	Day 225	Week 32
17	Day 233 – Day 246	Day 239	Week 34
18	Day 247 – Day 260	Day 253	Week 36
19	Day 261 – Day 274	Day 267	Week 38
20	Day 275 – Day 288	Day 281	Week 40
21	Day 289 – Day 302	Day 295	Week 42
22	Day 303 – Day 316	Day 309	Week 44
23	Day 317 – Day 330	Day 323	Week 46
24	Day 331 – Day 344	Day 337	Week 48
25	Day 345 – Day 358	Day 351	Week 50

CONFIDENTIAL Page 43 of 139

26	Day 359 – Day 372	Day 365	Week 52	
27	Day 373 – Day 386	Day 379	Week 54	
28	>=Day 387	Day 393	Week 56	

\* Day 1 is the date of randomization. Baseline is defined as the most recent assessment on or before day 1.

The assessment date is the scheduled date based on a bi-weekly interval.

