### 7.5.2. Quality of Life Questionnaire – Bronchiectasis

The QOL-B is a validated, self-administered PRO that assesses symptoms, functioning, and health-related quality of life for subjects with NCFBE (Quittner et al., 2015). The QOL-B contains 37 items in 8 domains (Respiratory Symptoms, Physical Functioning, Role Functioning, Emotional Functioning, Social Functioning, Vitality, Health Perceptions and Treatment Burden).

The QOL-B page 1 (demographics page) will be removed as demographics are collected on a separate eCRF page. The modified QOL-B, where validated translations are available in the local language, will be provided to all adult subjects in an electronic format on an electronic diary after randomization. Subjects will be required to complete the QOL-B after the training and prior to the administration of the first dose of their assigned study drug at Visit 2 (Day 1; Baseline). Subjects will complete the questionnaire directly on the electronic diary every 2 weeks from Day 1 to Week 56 (Table 5).

The subjects will complete the questionnaire while they are in the clinic if the study visit coincides with the availability of the questionnaire (in validated translation of the local language) and at home for the weeks in between the study visits. It is important for the site staff to remind the subjects to bring their electronic diaries with them to each clinic visit.

On days when the subject is at home (ie, days without study center visits), patient-reported outcome assessments are to be completed when they become available on the electronic diary.

The completed questionnaires will be reviewed during each visit. Subjects will be retrained on how to complete the questionnaires correctly, if needed. For adults, the Respiratory Symptoms Domain score of the QOL-B will be assessed as a secondary endpoint, with the other domain scores of the QOL-B assessed as exploratory endpoints.

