# 6.4.2. Date of First / Last IP intake, Treatment Display in Data Tabulations, and Actual Treatment

Administration of IP is collected daily using an electronic diary. Participants are not able to enter missed doses retrospectively, while the very first dose may not be recorded. Participant's date of attending Visit 2 is used as the First Dose Date (SCH\_VS dataset [Visit Dataset]) as participants will receive their initial dose at the site. A date of first dose will be assigned only if records for IP administration were reported fulfilling the condition "Did you take your study medication today?" = "Yes" (for at least one record) in the drug administration form ("Dose Administration" within the Patient Cloud folder of the CRF). Participants attending Visit 2 but without any records in "Dose Administration" fulfilling the condition will be considered as not being treated with randomized IP.

The "Last dose date" entered in the EOT form will be used to determine the date of last administration of randomized IP.

If not stated otherwise, tabulations will be presented by treatment groups and overall using the following labelling throughout all displays:

- Brensocatib 10 mg;
- Brensocatib 25 mg;
- Placebo;
- All Participants (applicable study population summaries only, unless stated otherwise [see Section 6.9]),
- Pooled Brensocatib (applicable for all safety tables, unless stated otherwise).

The participant's actual treatment for the Safety, Pharmacodynamic, PK Concentration, and CT Scan Analysis Sets will be derived from exposure data. The Kit ID dispensed by the IRT and actual kit ID used will be recorded. If a participant's actual treatment is the same as the assigned treatment, then actual treatment is the assigned treatment. If a participant receives a study treatment that is different from the assigned treatment, then the following rule will apply:

• the actual treatment group will be set to placebo, brensocatib 10 mg or brensocatib 25 mg depending on the most common administered dose, regardless of the randomized treatment.

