## 6.4.3. Baseline Definition, Change from Baseline

According to Table 5 of the CSP ("Schedule of Assessments and Procedures"), the second visit (V2) is defined as "Baseline". However, the definition of the "Baseline" which is used to

CONFIDENTIAL Page 32 of 139

derive any changes of assessments during study conduct, e.g., laboratory parameters, depends on the timing of the first IP administration and can therefore be different from Baseline/Day 1/Visit 2. Therefore, unless otherwise stated, for the purpose of analysis baseline value is the last non-missing value prior to or at the date of the first dose of IP, considering also unscheduled visits. For participants who do not receive IP during the study, baseline is defined as the latest, non-missing collected value on or before Study Day 1.

Change from baseline will only be calculated for measures that have post-baseline records. Change from baseline is calculated as:

visit value – baseline value.

If either the baseline or visit value is missing, the change from baseline will be set to missing as well.

For summaries, whenever baseline is presented, the above baseline definition is used. That is, the baseline summary presented is in general not the summary of the (CSP defined) Baseline/Day 1 visit. Screening values will be listed but not summarized. Throughout the document, Baseline (capital B) refers to the visit Baseline/Day 1; baseline (lower case b) refers to the values derived using the baseline definition above.

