## 6.5. Visit Windowing

The CSP defines for each of the study visits from Visit 3 (Week 4, Day 28) to EOS (Visit 12, Week 56, Day 392), a  $\pm$ 7-day visit window. However, the visit schedule may not be followed due to various reasons such as patients travel arrangements, etc. The goal is to use all available data such as data from unscheduled visits to minimize missing data at scheduled, nominal visits. Therefore, programmatic visit windowing will be applied to analysis datasets preparation.

Based on the actual visit date, the actual measure will be allocated to the specific visit using visit intervals as specified in Table 4. After all observations have been evaluated following the defined visit intervals, it may appear that an interval has multiple (valid) observations for the same assessment within the same scheduled, nominal visit. For the analysis, one of these observations will be used while the selection will follow the below rules (in the sequential order given):

- Select the observation closest to the target Study Day,
- Select the latter observation if 2 observations are equally close to the target Study Day.

CONFIDENTIAL Page 36 of 139

Table 4:	Visit	Wind	owing
----------	-------	------	-------

Scheduled Visit (Nominal Visit)	Scheduled Visit Day (Study Day)	Visit Intervals
Screening		<= -1
Day 1	1	1
Week 4	28	2 to 49*
Week 10	70	50 to 91
Week 16	112	92 to 133
Week 22	154	134 to 175
Week 28	196	176 to 217
Week 34	238	218 to 259
Week 40	280	260 to 301
Week 46	322	302 to 343
Week 52	364	344 to 378
Week 56	392	>=379

\*Note: Visit windowing will not be applied to assessments completed every day, or every 2 weeks. Refer to PRO assessments as described in Section 6.7.5. Further, in cases where the first IP was administered after day of randomization, visit windowing will not overrule assignment of baseline record and windowing will not be applied. As an example, consider a participant with date of randomization at 22-Jul but IP administration was at 24-Jul. Data reported at date of IP administration would have analysis date equal to 3 (date – date of randomization + 1). If visit windowing applied, participants would not have a baseline. Therefore, visit windowing will not be applied for those records who fulfill the constraint of the baseline.

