#### 6.7.5.6. EQ-5D-5L

A sample of the EQ-5D-5L questionnaire is provided in Appendix F. The EQ-5D-5L questionnaire will be collected at Study Day 1, at Week 4, Week 16, Week 28, Week 40, Week 52 (EOT) and Week 56 (EOS). In case of assessments out of visit window, windowing will be applied as detailed in Section 6.5.

For calculation of the index score, the US value set will be used for all participants.

Baseline is defined as the most recent assessment on or before study day 1.

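### SAP Table 6 ties the QoL-B baseline to the randomization date rather than the first-dose date, so a valid pre-dose score is rejected whenever Visit 2 falls after randomization

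*SAP*

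**What the plan says.** SAP 6.7.5.1 sets the windows for QoL-B, PGI-S and PGI-C. Its Table 6 footnote reads "Day 1 is the date of randomization. Baseline is defined as the most recent assessment on or before day 1", and the first post-baseline window, labelled Week 2, covers Days 2 to 22.

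SAP 6.4.3 has a different general rule: "baseline value is the last non-missing value prior to or at the date of the first dose of IP". For participants never dosed it falls back to Study Day 1. The rule gives way where another section sets its own definition, as Table 6 does.

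On timing, Protocol 7.5.2 says the QoL-B "will be provided to all adult subjects in an electronic format on an electronic diary after randomization", to be completed at Visit 2 before the first dose. SAP 6.4.2 states: "Participant's date of attending Visit 2 is used as the First Dose Date".

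SAP 6.4.5 expects randomization and first dose to coincide at Visit 2 but allows for discrepancies. The note under Table 4 in SAP 6.5 works through one, with randomization on 22-Jul and first dose on 24-Jul, and warns: "If visit windowing applied, participants would not have a baseline". The note keeps such baseline records out of the windowing, but it first says that Table 4 windowing does not apply to daily or two-weekly assessments and refers the reader to 6.7.5.

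For EQ-5D-5L, SAP 6.7.5.6 says "Baseline is defined as the most recent assessment on or before study day 1"; 6.7.5.7 uses the same definition for QoL-PCD.

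**The concern.** No QoL-B is scheduled before randomization, so no earlier score can stand in. If Visit 2 comes after the randomization date, the only pre-dose score is dated Day 2 or later. Section 6.4.3 would accept it as baseline; Table 6 does not.

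Under 6.4.3 a missing baseline makes every change from baseline missing. In SAP 8.3.5.1 baseline is also a model covariate. The participant therefore leaves the Family 6 comparisons, H11 and H12, although the On-Study estimand is meant to use all observed data. SAP 8.3.5.4 also excludes participants without a baseline score from the responder analysis. For an affected participant the loss is complete, and it comes from a dating rule rather than from uncollected data.

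**Working it through.** **1. The SAP's own example.** Study day = (date of interest − date of randomization) + 1 (SAP 6.4.5). With randomization on 22-Jul and first dose on 24-Jul, 24 − 22 + 1 = 3. This reproduces the Day 3 in the Table 4 note.

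**2. The same record under each rule.** Since the first-dose date is the Visit 2 date, the QoL-B completed at that visit is also dated Day 3.

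| Rule | Latest day accepted as baseline | Day 3 QoL-B |
|---|---|---|
| SAP 6.4.3 | first-dose date (Day 3) | baseline |
| SAP Table 6 | randomization date (Day 1) | not baseline; falls in Days 2 to 22 |

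**3. Other lags.** A lag of 1 to 7 days puts the Visit 2 QoL-B on Days 2 to 8, always inside Days 2 to 22 and never at baseline. At lag 0 it is on Day 1 and qualifies.

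**4. Does the Table 4 note rescue it?** The note protects records that meet the baseline definition. For QoL-B that definition is the Table 6 footnote, which a Day 3 record fails. Section 6.7.5 has no protection of its own.

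**5. Size.** The documents do not say how many participants have Visit 2 after randomization, so the affected share f is an assumption. Number lost = 1620 × f. Standard-error ratio = 1/√(1 − f).

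| f (assumed) | Adults lost | Standard-error ratio |
|---|---|---|
| 0.5% | 8 | 1.0025 |
| 1% | 16 | 1.005 |
| 2% | 32 | 1.010 |

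No power is stated for QoL-B. If it were 80% at two-sided 0.05, ignoring multiplicity, it would become Φ[(1.960 + 0.842)√(1 − f) − 1.960], which is 79.6% at f = 1% and 79.2% at f = 2%.

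The figure of 1620 is an upper bound on the adults concerned, because the QoL-B is given only where a validated translation exists (Protocol 7.5.2).

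**The case against.** **The trigger is off schedule.** Protocol Table 5 places randomization at Visit 2, the visit at which the QoL-B is completed. A participant handled to plan has both on one date. Taking the first tablet late after Visit 2 does no harm, because the SAP still uses the Visit 2 date, and a QoL-B completed on the randomization date would still qualify. This stands: the number affected may be near zero.

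**Table 6 agrees with Protocol 10.3**, which sets baseline at or before randomization. That is correct, but 10.3 permits exceptions. SAP 6.4.3 moved the general rule to first dose, and the Table 4 note protects late-dose baselines. Leaving QoL-B on the other anchor is an inconsistency for which no reason is given.

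**Other text might cover it.** The second part of the Table 4 note could be read as a general principle, but it still depends on the record meeting the baseline definition. A line under Table 6 equates the assessment date with the scheduled date, which might date a late Visit 2 form as Day 1. It more naturally explains the target-date column, since the rule in 6.7.5.2 of choosing the record closest to target presupposes actual dates.

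**Stronger readings that the documents do not support:**

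- A reader might infer a sizeable loss. A share of 5% would mean 81 adults and a standard error 2.6% higher, but nothing in the documents supports a share that large.
- A reader might infer that the pre-dose score contaminates the Week 2 result. Without a baseline there is no change score, so the record cannot enter the change model.
- A reader might infer bias between arms. The loss depends on visit logistics before dosing in a blinded trial, and no mechanism for bias is apparent.
- A reader might infer that EQ-5D-5L and QoL-PCD lose the same participants. Both are exploratory, and 6.7.5.6 sends EQ-5D-5L windowing to Section 6.5, where the protective note sits, so the effect there is unclear.

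**Conclusion.** The point holds as a specific inconsistency with a narrow trigger. When Visit 2 falls after randomization, Table 6 as written rejects a valid pre-dose QoL-B score that 6.4.3 would accept. The participant is then lost to the main test of an endpoint in the multiplicity-controlled hierarchy and to its responder analysis. The Table 4 note shows that the SAP recognised this trap for other assessments but did not clearly close it for QoL-B.

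The expected effect is small: a standard-error increase of about 0.3% to 1% under an assumed 0.5% to 2% affected, with no bias shown. The conclusion assumes that QoL-B records are dated by actual completion and that none was completed on the randomization date.

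There is one further mismatch. The tipping-point code, which the SAP applies to QoL-B as well, lists baseline among the variables to be imputed. The sensitivity analysis could therefore retain participants whom the main analysis drops.

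**What to change.** 1. In the Table 6 footnote, define baseline as in SAP 6.4.3: the last assessment on or before the first-dose date, or on or before the randomization date for participants never dosed.
2. State that Table 6 windowing does not override the baseline record.
3. Record this in SAP Section 13 as a departure from the randomization-date baseline in Protocol 10.3.
4. For consistency, align the study-day-1 wording for EQ-5D-5L (6.7.5.6) and QoL-PCD (6.7.5.7).

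The cost is a few sentences of SAP text and a small change to the program that builds the questionnaire analysis dataset. No new data are needed. Counting participants whose Visit 2 date is later than their randomization date requires no treatment codes, so the sponsor can size the issue while blinded, before database lock.
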